13 STUDY STOPPING RULES

Additional Interim Safety Assessment (Study Sample Size: 15 patients)

An interim assessment for toxicity and early mortality will be performed after the first 5 patients have enrolled, and again after the first 10 patients are enrolled. Accrual may proceed to a maximum of 15 patients, if the stopping rules are not met within the first 5 patients

The study may be halted for further review if, for any reason involving subject safety, the PIs and Medical Monitors deem continuing the study inappropriate. The following scenarios will also result in temporarily halting the study for further review: 1) major bleeding event in more than 2 of first 10 patients on protocol (as defined as fatal bleeding and/or symptomatic bleeding in a critical area or organ, such as intracranial, intraspinal, intraocular, retroperitoneal, intraarticular or pericardial, or intramuscular with compartment syndrome and/or bleeding causing a fall in hemoglobin level of 2g/dL or more, or leading to transfusion of two or more units of whole blood or red cells). This bleeding definition is congruent with International Society of Thrombosis and Hemostasis (ISTH) definition of major bleeding. An incidence of > 20% hemorrhagic complications would be unacceptable in this setting. Thus, we will continually monitor the observed proportion of patients with major bleeding complications. We start with prior Beta distribution, which has mean 0.2. If ever we have more than 80% posterior probability that the true proportion is greater than 0.20, accrual to the protocol will be suspended to allow the MM and PIs to review the incidence of major bleeding. 2) We will also continually monitor the study for excessive Day 15 mortality. In parallel with our decision rule related to excessive severe hemorrhagic events, we will suspend accrual if we see if we see at least five deaths by Day 15 among the first six patients, or at least seven deaths by Day 14 among the first eleven patients. If the true Day 14 mortality rate is 70% (which is the historical rate for patients with respiratory compromise), the study has a probability of 0.80 of being suspended. Conversely, if the Day 14 mortality rate is 50%, the study has a much lower probability of 0.30 of being suspended.

In the event of temporary halt of the study, the PI's, medical monitor, and independent medical monitor will meet to review the data and discuss relatedness to study drugs and determine next necessary steps. If the study is halted or terminated, a written statement fully documenting the reasons for study halt or termination and subsequent decisions of study execution will be communicated to the IRB and appropriate regulatory authorities.

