12.1.2. Additional Interim Safety Assessment (Study Sample Size: 15 patients)

An interim assessment for toxicity and early mortality will be performed after the first 5 patients have enrolled, and again after the first 10 patients are enrolled. Accrual may proceed to a maximum of 15 patients, if the stopping rules are not met within the first 5 patients.

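### The two bleeding triggers in Section 13 are not consistent: 3 of 10 halts the study, but the stronger signal 4 of 13 halts it under no Beta prior with mean 0.2

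*Combined protocol and SAP*

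**What the plan says.** Section 13 sets the limit: "An incidence of > 20% hemorrhagic complications would be unacceptable in this setting". It then gives two numerical triggers for it.

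- A count: the study is temporarily halted for a "major bleeding event in more than 2 of first 10 patients on protocol", that is, at 3 of 10.
- A posterior rule: "We start with prior Beta distribution, which has mean 0.2", and "If ever we have more than 80% posterior probability that the true proportion is greater than 0.20, accrual to the protocol will be suspended". It is applied throughout, since "we will continually monitor the observed proportion of patients with major bleeding complications".

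Sections 12.1.2 and 13 schedule the interim looks: "An interim assessment for toxicity and early mortality will be performed after the first 5 patients have enrolled, and again after the first 10" patients. They also state that "Accrual may proceed to a maximum of 15 patients", provided that no stopping rule is met in the first 5. No count and no scheduled look is given for patients 11 to 15.

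Section 13 also allows a halt at any time for any safety reason. Section 14 requires ongoing review of all SAEs, regular review of all clinical data, and recommendations on continuation or suspension at monthly meetings.

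**The concern.** Two rules that serve one limit should order the evidence in the same way. Here the count clause halts at 3 of 10. Once it has expired, the posterior rule lets accrual continue at a result that points more strongly to a rate above 20%.

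Take bleeds in patients 4, 8, 11 and 13. No trigger fires at any step, and the trial stands at 4 of 13 (30.8%) with no mandatory pause. Had the third bleed come in patient 10, the trial would have halted at 30.0%.

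At stake is whether the automatic bleeding safeguard is coherent over the last third of accrual, in a trial whose primary endpoint is safety.

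**Working it through.** **Inputs.** From Section 13: limit 0.20, posterior threshold 0.80, prior mean 0.2, count clause 3 or more among the first 10. From Sections 12.1.2 and 13: maximum of 15 patients. The readable text gives no prior weight m (the sum of the two Beta parameters), so every m is considered.

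**Method check on the plan's own figures.** Section 13 gives suspension probabilities only for its mortality rule (5 or more deaths in 6, or 7 or more in 11). The formula is P(X6 ≥ 5) + Σ P(X6 = x) × P(Y5 ≥ 7 − x) over x ≤ 4, where X6 and Y5 are binomial counts in the first 6 and the next 5 patients.

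- True 70%: 0.4202 + 0.3791 = 0.799 (stated 0.80).
- True 50%: 0.1094 + 0.1831 = 0.292 (stated 0.30).

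The method reproduces the plan's figures. No such figures are given for bleeding.

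**Posterior for bleeding.** The prior is Beta(0.2m, 0.8m). After x bleeds in n patients the posterior is Beta(0.2m + x, 0.8m + n − x). For the counts below, P(rate > 0.20) falls steadily as m rises, so its maximum is the limit m → 0, which equals P(Bin(n − 1, 0.2) ≤ x − 1). For 3 of 10 this is P(Bin(9, 0.2) ≤ 2) = 0.738; for 4 of 13, P(Bin(12, 0.2) ≤ 3) = 0.795; for 4 of 14, P(Bin(13, 0.2) ≤ 3) = 0.747.

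| Result | Raw proportion | Maximum posterior | m = 1 | m = 5 | m = 15 | P(this many or more) at a true 20% |
|---|---|---|---|---|---|---|
| 3 of 10 | 30.0% | 0.738 | 0.728 | 0.698 | 0.656 | 0.322 |
| 4 of 13 | 30.8% | 0.795 | 0.786 | 0.758 | 0.713 | 0.253 |
| 4 of 14 | 28.6% | 0.747 | 0.740 | 0.716 | 0.678 | 0.302 |

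- None of the three reaches 0.80 under any weight, so 3 of 10 halts only through the count clause.
- 4 of 13 is stronger than 3 of 10 on all three scales. Its posterior is higher at every m, by up to 0.060.
- 4 of 14 is slightly stronger by posterior at every m (by at most 0.023) and by exact tail, but lower as a raw proportion.
- 3 of 11 and 4 of 15 have a lower posterior than 3 of 10 at every m.
- 4 of 12 halts only if m is below about 4.7.

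**Size.** An exact patient-by-patient recursion halts if the posterior exceeds 0.80, or if there are 3 or more bleeds with n ≤ 10. The comparison adds a halt at 4 or more bleeds for n = 11 to 14. Patient 15 is left out because accrual ends there. Probability of suspension by patient 14, m = 5 (assumed):

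| True rate | As written | 3-of-10 level carried forward | Difference |
|---|---|---|---|
| 10% | 0.084 | 0.094 | 0.010 |
| 20% | 0.350 | 0.401 | 0.050 |
| 30% | 0.652 | 0.719 | 0.067 |
| 40% | 0.862 | 0.907 | 0.045 |

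(Differences are taken before rounding.) Over weights 1 to 15, the difference is 0.046 to 0.071 at a true 30% and 0.031 to 0.048 at 40%.

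**The case against.** **Review does not stop at patient 10.** A reader might infer that bleeding after patient 10 goes without required review. Section 14 does not support that. SAE review, review of clinical data and monthly recommendations on suspension are all required, and largely by the people who would review a triggered halt. Only the automatic pause is lost. This stands and narrows the point.

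**The posterior rule itself does not loosen.** It is the same for all 15 patients; an additional early count expires. Stricter protection during first exposure is a legitimate design, and nothing in Section 13 says that the 3-of-10 evidence level was meant to carry on. This stands too. But the plan does not say that the expiry is intended, and it gives no suspension probabilities from which a reader could see it.

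**The count might merely illustrate the posterior rule.** It cannot: no Beta prior with mean 0.2 makes that rule fire at 3 of 10. For weights from 0.01 to 10 it needs 4 of 10. On that reading the two statements conflict outright.

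**The Beta parameters may have been lost from the readable text.** Possibly, but the inconsistency holds for every weight.

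**The size is easily overstated.** Given no halt by patient 10, the chance of a halt at patients 11 to 14 is 0.05 to 0.08 as written against 0.22 to 0.24 carried forward (true 30%, weights 1 to 15). A reader might take that contrast as the overall effect. It applies only to the 31 to 38% of trials still unhalted at patient 10.

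**Conclusion.** The two triggers are inconsistent, whatever the prior weight. The mandatory rule halts at 3 of 10 and not at 4 of 13, which is stronger evidence by every measure used. The case of 4 of 14 is weaker and depends on the scale, so it should not be put on a par with 4 of 13.

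The practical effect is modest: at weight 5, about 7 more suspensions per 100 trials at a true 30% and 4 to 5 at 40% if the evidence level is carried forward. The figures assume that either trigger alone suffices, a prior weight that the readable text does not give, and that each patient's bleeding status is known before the next enrols. With 7 days of dosing and 28 days of adverse event collection, patients may overlap, so the gains are upper bounds. A halt at patient 13 or 14 can spare at most two patients or one, and it is a temporary pause.

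The documents do not show that safety oversight is missing after patient 10, or that an early rule which expires is an error. They leave the two triggers unreconciled. The correction is worthwhile because it is cheap and concerns a stated safety boundary.

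**What to change.** In Section 13, reconcile the two bleeding triggers over all 15 patients, in one of two ways.

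1. Carry the 3-of-10 evidence level forward, for example by adding that a fourth major bleed by patient 14 also suspends accrual. This does not depend on the prior weight: 4 of 12, 4 of 13 and 4 of 14 all exceed the 3-of-10 posterior for every Beta prior with mean 0.2.
2. If a stricter early rule that ends at patient 10 is intended, say so and report the resulting suspension probabilities, as is done for mortality.

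In either case, confirm that both Beta parameters are stated and that either trigger alone suffices.

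The change takes two or three sentences and no added data or visits. Under the first option, at weight 5, about one more temporary pause per 100 trials is expected at a true 10% rate and about five per 100 at 20%. The second option adds no pauses.

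### Section 13 says mortality is monitored continually in a 15-patient study, but its last numerical boundary is at patient 11, so up to 10 deaths in 15 need not force a suspension

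*Combined protocol and SAP*

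**What the plan says.** Section 13 (Study Stopping Rules) sets the study size: "Accrual may proceed to a maximum of 15 patients". On mortality it says: "We will also continually monitor the study for excessive Day 15 mortality". Two boundaries follow, and reaching either suspends accrual: "at least five deaths by Day 15 among the first six patients", or "at least seven deaths by Day 14 among the first eleven patients".

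The same section gives the rule's operating characteristics. The first case is introduced by "If the true Day 14 mortality rate is 70% (which is the historical rate for patients with respiratory compromise", and its suspension probability is 0.80. The second is "if the Day 14 mortality rate is 50%, the study has a much lower probability of 0.30 of being suspended".

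The scheduled reviews also stop early: "An interim assessment for toxicity and early mortality will be performed after the first 5 patients have enrolled, and again after the first 10 patients". Section 12.1.2 repeats this schedule and ties continued accrual to the first five patients only: "Accrual may proceed to a maximum of 15 patients, if the stopping rules are not met within the first 5 patients". No section gives a mortality boundary that uses deaths after patient 11.

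Three other provisions bear on the point.

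- Section 13 lets the principal investigators and medical monitors halt the study for any safety reason.
- Section 14 requires ongoing review of serious adverse events and monthly meetings that can recommend suspension.
- The bleeding rule in Section 13, which the mortality rule is said to parallel, is a posterior-probability rule that can fire at any patient count.

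**The concern.** A reader of Section 13, including an ethics board, would take continual monitoring to mean that a death anywhere in the 15-patient cohort counts toward a pre-specified limit, as a major bleed does under the neighbouring rule. For mortality that is true only up to patient 11.

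The rule can then contradict its own threshold. It treats 7 deaths in 11 as enough to suspend, but a higher proportion over the full cohort may trigger nothing. Safety is the primary objective, so a pre-specified safeguard should either cover the cohort it is said to cover or state where it ends.

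**Working it through.** **Inputs (Section 13).** Maximum of 15 patients. Suspend if X6 ≥ 5 or X11 ≥ 7, where Xn is the number of deaths among the first n patients. Reference mortality rates are p = 0.70 and p = 0.50. The 60% row below is an added intermediate value. I assume independent patients with a common rate p, and outcomes known at each look.

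**Step 1: reproduce the plan's figures.**
P(suspend) = P(X11 ≥ 7) + P(X6 ≥ 5 and X11 ≤ 6).

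The second term has 6 sequences with 5 deaths (5 in the first six, none in the next five). It has 31 with 6 deaths (6 × 5 = 30 with 5 then 1, plus 1 with 6 then 0). It is therefore 6p⁵(1−p)⁶ + 31p⁶(1−p)⁵.

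- At p = 0.70: 0.7897 + (0.0007 + 0.0089) = 0.7993. The plan states 0.80.
- At p = 0.50: 0.2744 + 37/2048 = 0.2744 + 0.0181 = 0.2925. The plan states 0.30.

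Both figures reproduce from the looks at 6 and 11 alone, so the stated probabilities contain no later boundary. Checking after every death up to patient 11 gives the same values, because a death count never falls.

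**Step 2: the most deaths that escape.** Without suspension there are at most 6 deaths in the first 11, with at most 4 of them in the first 6. If patients 12 to 15 all die, the total is 6 + 4 = 10 of 15, or 66.7%. The triggering level is 7/11 = 63.6%. Eleven or more deaths in 15 always trigger the rule.

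**Step 3: how likely that is.** There are C(11,6) = 462 sequences with 6 deaths in 11. Of these, 31 have already triggered at patient 6, leaving 431.
P(10 deaths, no suspension) = 431p¹⁰(1−p)⁵.

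- At p = 0.70 this is 0.0296, and at p = 0.50 it is 0.0132.
- The expression is largest at p = 2/3, where it is 431 × 1024/14,348,907 = 0.031. No constant mortality rate makes the event more likely than that.

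**Step 4: an illustrative extension.** Suppose suspension also followed 9 deaths in the first 14 (64.3%, against 63.6% for 7/11). In a study not yet suspended, this needs exactly 6 deaths in the first 11 and then deaths in patients 12, 13 and 14. The added probability is 431p⁹(1−p)⁵.

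| True mortality | X6 ≥ 5 | X11 ≥ 7 | Either (rule as written) | 10 of 15, no suspension | Added by 9 of 14 | Rule with 9 of 14 |
|---|---|---|---|---|---|---|
| 50% | 0.1094 | 0.2744 | 0.2925 | 0.0132 | 0.0263 | 0.3188 |
| 60% | 0.2333 | 0.5328 | 0.5495 | 0.0267 | 0.0445 | 0.5940 |
| 70% | 0.4202 | 0.7897 | 0.7993 | 0.0296 | 0.0423 | 0.8416 |

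With the extra boundary, 10 of 15 without suspension becomes impossible, because every such sequence passes through 9 of 14.

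**The case against.** The strongest reply is that the rule suspends accrual, so it protects patients not yet enrolled. On that view the boundary at 11 exists to protect patients 12 to 15. It may still fire while they are being enrolled, since deaths by Day 14 or 15 take time to mature. Patient 15's own outcome can never inform accrual. This stands. A reader might infer that 4 of 15 patients (27%) are left unprotected, but the documents do not support that. What is missing is any numerical use of those patients' deaths.

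A reader might also infer that nobody watches mortality after patient 11. That is not supported either. Deaths are serious adverse events, reported to the principal investigator within 24 hours whatever their cause (Sections 8.2.2 and 8.4). The discretionary halt (Section 13) and the reviews in Section 14 also run throughout. These provisions are matters of judgement, however, while reaching a numerical boundary obliges suspension.

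It is also fair to say that ending formal looks early in a small pilot is defensible, and that the practical gain is small. The illustrative boundary fires only at patient 14, could spare only the enrolment of patient 15, and needs the preceding outcomes to be known in time. All of this stands, and it limits the point's weight. It does not remove the mismatch between the description of the monitoring and the rule given.

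**Conclusion.** The point holds as a minor inconsistency. The numerical mortality rule ends at patient 11 of 15, while the text describes continual monitoring alongside a bleeding rule that has no such end. As written, 10 of 15 deaths (67%) can pass without a mandatory suspension although 7 of 11 (64%) cannot. The chance of that outcome is about 0.03 at 70% mortality, 0.013 at 50%, and at most 0.031 at any constant rate.

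It would be wrong to conclude that the stated 0.80 and 0.30 are in error. They are right for the two boundaries given and need changing only if a boundary is added.

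The results rest on independent outcomes, a common mortality rate and outcomes known at each look. Slower maturation of outcomes would reduce what any later boundary can achieve.

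Section 12.3 still refers to twelve patients. A rule ending at patient 11 would suit a study of that size, so the boundaries may not have been updated for 15. That is an inference, not something the documents state.

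**What to change.** Either of two changes to Section 13 resolves the point. The choice, and any boundary, is for the sponsor.

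1. Extend the numerical mortality rule past patient 11 at a level consistent with the plan's own threshold, and restate the suspension probabilities for the full rule. As an illustration only, adding 9 of the first 14 changes 0.80 to 0.84 at 70% mortality and about 0.29 (stated as 0.30) to 0.32 at 50%. The cost is one clause, two restated probabilities and about 3 points more suspension at 50%. The text should acknowledge that such a boundary can act only before patient 15 is enrolled.
2. Otherwise, remove the word *continually* and state that the numerical rule ends at patient 11, with the discretionary halt and Section 14 review applying thereafter. This is a change of wording only, and the stated probabilities stay as they are.

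Under either option, reconcile two related inconsistencies at the same time: the mixture of Day 14 and Day 15 mortality within the rule, and the twelve patients in Section 12.3 against the 15 stated elsewhere.

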COVID-19 ARDS appears to have worse outcomes than ARDS from other causes. The intensive care unit and hospital mortality from typical ARDS are 35.3% (95% CI, 33.3–37.2%) and 40.0% (95% CI, 38.1–42.1%), respectively.⁶ For COVID-19 ARDS, mortality ranged between 26% and 61.5% if ever admitted into a critical care setting, and in patients who received mechanical ventilation, the mortality can range between 65.7% to 94%. Risk factors for poor outcomes include older age; presence of comorbidities such as hypertension, cardiovascular disease and diabetes mellitus; lower lymphocyte counts; kidney injury; and raised D-dimer levels. Death from COVID-19 ARDS is due to respiratory failure (53%), respiratory failure combined with cardiac failure (33%), myocardial damage and circulatory failure (7%), or death from an unknown cause.⁷

Given the high mortality rate associated with COVID-19 ARDS, preventing progression of COVID-19 pneumonia in patients simply requiring supplemental oxygen to COVID-19 ARDS is a key priority and goal.

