4.2 Exclusion Criteria

1. In the opinion of at least one investigator, unlikely to survive for >48 hours from screening.
2. Severe chronic respiratory disease (e.g. COPD or other) requiring supplemental oxygen and/or having required mechanical ventilation pre-COVID-19 infection.
3. Concurrent enrollment in a COVID related interventional drug trial. Use of remdesivir, steroids, and convalescent plasma are permitted along with other standard of care therapies for COVID.³⁷
4. Currently on invasive mechanical ventilation.
5. Hypotension defined as systolic blood pressure < 90 mmHg on two sequential readings at least 4 hours apart.
6. Total Bilirubin ≥ 3 x upper limit of normal (ULN), Creatinine Clearance ≤ 30 mL/min/1.73m².
7. Pregnant or breastfeeding.
8. Known diagnosis of an acute thrombosis on admission.
9. Concurrent dual antithrombotic therapy (aspirin or P2Y₁₂ inhibitor plus anticoagulation to treat deep venous thrombosis or pulmonary embolism (single antiplatelet or anticoagulant agent at prophylactic dose is permitted).
10. Concomitant use of thrombolytic therapy.
11. Concomitant therapeutic systemic anticoagulant therapy (e.g. heparin, warfarin, direct thrombin inhibitors and direct factor Xa inhibitors). As per NIH Guidelines: Hospitalized adults with COVID-19 should receive VTE prophylaxis per the standard of care for other hospitalized adults (AIII). Anticoagulant or antiplatelet therapy should not be used to prevent arterial thrombosis outside of the usual standard of care for patients without COVID-19 (AIII); <https://www.covid19treatmentguidelines.nih.gov/therapeutic-management/>
12. History of recent major bleeding, defined in accordance with the criteria of the International Society on Thrombosis and Hemostasis (ISTH).
13. History of bleeding disorder thought to impose excessive bleeding risk as per investigator discretion
14. Hemodynamic instability, defined as inability to maintain mean arterial pressure.
15. Hypersensitivity to the active substance or to any of the excipients of uproleselan.
16. Any physical examination findings and/or history of any illness that, in the opinion of the investigator, might confound the results of the study or pose an additional risk to the patient by their participation in the study

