5.1 Treatment Dosage and Administration

Protocol treatment must start within 48 hours of the admitted patient requiring supplemental oxygen for documented COVID-19 pneumonia. Study enrollment is defined as the day subject meets all of the inclusion criteria and none of the exclusion criteria.

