14 DATA AND SAFETY MONITORING

The Data Safety and Monitoring Plan (DSMP) will consist of an independent Medical Monitor (a physician from UMHS) who will work with the PIs to evaluate AEs. The Investigators and Medical Monitors will perform ongoing review of all SAEs in a timely fashion, and regular reviews of all clinical data (including AEs and lab data) throughout the study. Any concerns for safety by any of these parties will be communicated to the other parties immediately for discussion. The investigators and co-investigators will meet monthly during the study and will allocate adequate time for such monitoring activities. They will review expected and unexpected adverse events, safety concerns, adherence to protocol therapy, study enrollment, and any potential protocol amendments that may be required. Recommendations for study continuation, amendments, suspension and/or study termination will be made at each of the monthly protocol monitor meetings.

The investigators will also ensure that the monitor or other compliance or quality assurance reviewer is given access to all the above noted study- related documents and study related facilities (e.g., pharmacy, diagnostic laboratory, etc.), and has adequate space to conduct the monitoring visit. If while following the Data Safety and Monitoring Plan (DSMP), as outlined in [Section 8.5](#), there is a pattern of unexpected and concerning AE or a SAE then, there would be a consideration to create a Data and Safety Monitoring Board (DSMB).

REFERENCES

1. Fan E, Brodie D and Slutsky AS. Acute Respiratory Distress Syndrome: Advances in Diagnosis and Treatment. *JAMA*. 2018;319:698-710.

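### The Section 13 mortality rule is calibrated to an unsourced 70% death rate, so it almost never acts (probability 0.03 or less) at any true mortality up to 30%

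*Combined protocol and SAP*

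**What the plan says.** Section 13 sets a numeric mortality rule alongside a bleeding rule. It is introduced with "We will also continually monitor the study for excessive Day 15 mortality", and accrual is suspended on "at least five deaths by Day 15 among the first six patients, or at least seven deaths by Day 14 among the first eleven patients". The stated performance rests on two rates. The first reads "If the true Day 14 mortality rate is 70% (which is the historical rate for patients with respiratory compromise", with suspension probability 0.80. The second is 50%, with probability 0.30. No reference supports the 70%, and no probability is shown for any lower rate.

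Sections 12.1.2 and 13 also plan interim assessments of toxicity and early mortality after 5 and 10 patients, and let accrual run to 15 if the stopping rules are not met in the first 5.

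On the population, Section 5.1 says "Protocol treatment must start within 48 hours of the admitted patient requiring supplemental oxygen for documented COVID-19 pneumonia", and Section 4.2 excludes anyone "Currently on invasive mechanical ventilation". Section 1.1 puts COVID-19 ARDS mortality at 26% to 61.5% for patients ever in critical care, and says that "in patients who received mechanical ventilation, the mortality can range between 65.7% to 94" per cent.

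There is further, non-numeric cover. Section 13 allows a halt if "for any reason involving subject safety, the PIs and Medical Monitors deem continuing the study inappropriate". Section 14 adds "Recommendations for study continuation, amendments, suspension and/or study termination will be made at each of the monthly protocol monitor meetings". Section 8 requires serious adverse events to reach the principal investigator within 24 hours.

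**The concern.** A mortality rule protects patients only if its boundary relates to the death rate expected in the patients enrolled. Here the reference rate appears to belong to a sicker group. The 70% sits inside the protocol's ventilated range and 8.5 points above the top of its critical-care range (70 − 61.5). The link to ventilated patients is an inference, because the Section 1.1 figures are not given as Day-14 or Day-15 rates.

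The benchmark also has an awkward double role: it is called the historical rate, yet it is the rate the rule is built to catch. If 70% really were the baseline, a drug with no effect on mortality would suspend accrual 80% of the time. If the baseline is far lower, the rule hardly ever acts.

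Three smaller gaps are in the same text:

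- One limb counts deaths by Day 15 and the other by Day 14.
- There is no mortality boundary after patient 11.
- Boundaries at 6 and 11 do not line up with the assessments at 5 and 10, or with the sentence that conditions accrual to 15 on the first 5 patients. Continual monitoring partly covers this last gap.

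At stake is the only mortality threshold in a trial whose primary objective is safety.

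**Working it through.** **Inputs.** From Section 13: suspend at 5 or more deaths in the first 6, or 7 or more in the first 11; stated probabilities 0.80 at 70% and 0.30 at 50%; maximum 15 patients. From Section 1.1: 26% to 61.5% (critical care) and 65.7% to 94% (ventilated). Day-14 and Day-15 deaths are treated as the same event. Baseline mortality in enrolled patients is not in the documents, so it is varied.

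**Formula.** Let p be the true mortality and X the deaths among the first 6 patients. Then

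P(suspend) = P(X ≥ 5) + Σ over x = 0 to 4 of P(X = x) × P(Bin(5, p) ≥ 7 − x).

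Only x = 2, 3 and 4 contribute to the sum, because five more patients cannot lift 0 or 1 deaths to 7.

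**Reproducing the plan's figures.**

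- p = 0.70: 0.4202 + (0.0595 × 0.1681 + 0.1852 × 0.5282 + 0.3241 × 0.8369) = 0.4202 + 0.3791 = 0.799. The plan states 0.80.
- p = 0.50: 0.1094 + (0.2344 × 0.0312 + 0.3125 × 0.1875 + 0.2344 × 0.5000) = 0.1094 + 0.1831 = 0.292. The plan states 0.30.

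Both agree to within 0.01, so the rule has been read as intended.

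**Lower rates, same formula.** At p = 0.30: 0.0109 + (0.3241 × 0.0024 + 0.1852 × 0.0308 + 0.0595 × 0.1631) = 0.0109 + 0.0162 = 0.027.

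| True mortality | P(suspend) |
|---|---|
| 10% | 0.0001 |
| 15% | 0.0007 |
| 20% | 0.003 |
| 26% | 0.013 |
| 30% | 0.027 |
| 40% | 0.11 |
| 50% | 0.29 |
| 61.5% | 0.59 |
| 65.7% | 0.70 |
| 70% | 0.80 |

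The probability rises with p, so 0.027 is the maximum for any rate up to 30%. It reaches 0.10 only at 39% and 0.50 only at 58%.

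**Ability to flag harm, by assumed baseline.** Each entry is P(suspend) at twice or three times the baseline.

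| Baseline | Doubling | Tripling |
|---|---|---|
| 10% | 0.003 (at 20%) | 0.027 (at 30%) |
| 15% | 0.027 (at 30%) | 0.19 (at 45%) |
| 20% | 0.11 (at 40%) | 0.55 (at 60%) |
| 26% | 0.34 (at 52%) | 0.93 (at 78%) |
| 30% | 0.55 (at 60%) | not shown (90%) |

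**What the boundary permits.** Deaths of 4 in 6, then 6 in 11, then 10 in 15 never meet either limb. The last step needs all four of patients 12 to 15 to die. The probability of ending with 10 or more deaths without a trigger is 0.0004 at 30% mortality, 0.004 at 40% and 0.013 at 50%, with a peak of about 0.03 near 66%.

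**The case against.** The best reply is that a safety rule should seldom fire at acceptable mortality, so a low suspension probability up to 30% is a fault only if such rates are unacceptable in these patients. The documents do not say. Against the sponsor's own benchmark the rule is strict, because matching the historical rate suspends accrual with probability 0.80. Excluding patients ventilated at entry does not stop them being ventilated later, and the Section 1.1 ranges cannot settle the right benchmark in either direction. Fatal bleeds also count under the separate bleeding rule, interim assessments name early mortality, and in an open-label trial of 15 every death will be looked at. The path to 10 of 15 deaths is rare.

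Much of this stands as qualification. The baseline is unknown, the rule works better from 26% upward, and the discretionary safeguards are real. It does not rescue the rule. The missing expected mortality is part of the defect, because without it nobody can judge whether 70% and 50% are sensible anchors. None of the other safeguards carries a mortality threshold, and the bleeding rule covers one cause of death. Reading 70% as the true baseline only exposes the other fault: a drug with no mortality effect would usually trigger suspension.

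**Conclusion.** The concern holds and should be fixed before the rule is relied on. The protocol's arithmetic is right; its reference rate is unsupported for the patients enrolled. As written, the rule suspends with probability at most 0.027 for any true mortality up to 30%, and with probability 0.013 to 0.59 across the protocol's critical-care range.

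These probabilities are exact for the written rule, given independent outcomes with a common death rate and one horizon for both limbs. How serious the weakness is depends on the baseline, which is an assumption: detection of a doubling or tripling is poor from 10% to 15% and considerably better from 26%. The criticism is confined to the numeric rule and does not imply that deaths would go unreviewed.

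**What to change.** Amend Sections 13 and 12.1.2 as follows. The sponsor chooses the rates and the boundary.

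1. Replace the 70% and 50% anchors with acceptable and unacceptable Day-15 mortality for patients who meet Section 4, with a source. The institutional pool that supplies the control cohort is one candidate.
2. Re-derive the boundary so that it also covers patients 12 to 15, and print exact suspension probabilities over a range such as 10% to 70%.
3. Use a single horizon throughout.
4. Reconcile the boundaries with the assessments at 5 and 10, and the sentence about the first 5 patients with the later limb that also suspends accrual.

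This needs wording and a binomial table, with no extra patients or procedures. The real cost is more temporary pauses when the drug is safe, and the table should show it. For illustration only, a boundary of 3 or more deaths in 5, or 4 or more in 10, pauses with probability 0.02 at 10% mortality, 0.06 at 15%, 0.14 at 20%, 0.27 at 26%, 0.37 at 30% and 0.64 at 40%. If 26% to 30% were acceptable, that boundary would pause too often and a looser one would be needed. It also stops at patient 10, so it would itself have to be extended.
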